4.1 Prospective track

Regarding the prospective track (**Figure 6**), each month from September 2020 to May 2022 (20 months), twelve laboratories listed in **Table 1** committed to send the first 15 unduplicated isolates of *S. pneumoniae* collected from patients meeting the following criteria:

Inclusion criteria:

- Patients living in Belgium at the time of the study,
- from whom unduplicated *S. pneumoniae* isolates were collected in routine practices,
- from non-invasive upper (e.g.: pus/fluid from nasal sinus or from otitis media fluid) or lower respiratory tract (e.g. sputum bronchial or endotracheal aspirate, bronchoalveolar fluid (BAL),...) clinical samples.
- from patients diagnosed with pneumonia, sinusitis and otitis.

Exclusion criteria:

- Patients for whom *S. pneumoniae* was simultaneously isolated from blood or another usually sterile specimen.

Consequently, a theoretical maximal amount of 3,600 non-invasive *S. pneumoniae* isolates will be prospectively collected, although the actual number will probably be lower given the lower prevalence of NIPD during the summer period. For every shipped strain (with associated metadata) during the study period, the laboratory will be compensated by payment of €20.

The transfer of the isolates (under dry ice) from hospital laboratories to the “Sciensano Unit ‘Antibiotics & Resistance’ (Site Engeland - [name])” will be organised in the last week of every month, using the Sciensano internal sample transport service. Isolates will be accompanied by an electronic record sheet, listing the following metadata **upon availability** :

- isolate number
- Hospitalised (HOS), residing in a long-term care facility (LCF), ambulatory (AMB), or other (to be specified).
- admission date (hospitalised patients only)
- date of specimen collection
- patient age
- patient sex
- sample source including collection method
- clinical diagnosis
- vaccination status of the patient for *Streptococcus pneumoniae*
- For bacterial cultures from sputum, the amount of epithelial cells and white blood samples
- Other potential respiratory pathogens isolated (e.g. *H. influenzae*, *M. pneumoniae*, ...)

For all isolates sent, following analyses will be performed at Sciensano:

- Identification and confirmation of isolates by reference methods prior to use.
- Capsular typing using an FT-IR based method that will be developed in the scope of the project (section 5.4).
- Characterization of NeSP strains by gene sequencing of the *cps* locus.
- Antibiotic susceptibility tests by microdilution (MIC).
- Whole-Genome Sequencing (WGS) for multi-drug resistance and non-typeable strains or if clonality of the same serotypes originating from different, but geographically linked, patients needs to be assessed.

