1.1 Pneumococcal vaccination programs reduced burden of invasive disease

Streptococcus pneumoniae is a leading cause of morbidity and mortality worldwide among children <2 years of age and in the elderly [1]. The pathogenicity of this bacteria can be divided into 2 forms: invasive (IPD) and non-invasive pneumococcal disease (NIPD). Whereas the dangerous IPD type is responsible for meningitis and bacteraemia (septicaemia), the less severe NIPD can cause upper and lower respiratory tract infections such as community acquired pneumonia (CAP) and otitis media (OM). Of note, this subdivision between IPD and NIPD pneumococcal diseases is somewhat arbitrary since a substantial proportion (10-20%) of CAP pneumonia caused by *S. pneumoniae* is associated with contemporary bacteraemia (especially in elderly and debilitated patients). The distinction between PID and NIPD relates to the laboratory diagnosis and anatomical sites from which pneumococci are isolated. In PID, *S. pneumoniae* is detected from normally sterile body fluids (blood, cerebrospinal fluid (CSF), pleural, peritoneal or articular fluids). In NIPD, pneumococcal isolates are typically isolated from superficial body sites such as ear, nose, sputum or other lower respiratory tract sites (bronchial, endotracheal aspirates, bronchoalveolar lavage,...). There are over 90 pneumococcal serotypes, classified by an immunologically distinct capsule encoded by the capsular polysaccharide (*cps*) biosynthesis locus of the genome. The capsule is a major virulence factor and the basis for the currently licensed vaccines targeted toward the paediatric and elderly communities.

In the course of the decades, various pneumococcal conjugate vaccines were successively introduced, with the 7-valent PCV7 vaccine gradually being replaced by the 10-valent PCV10 and the 13-valent PCV13 [4]. These vaccination programs have led to drastic changes in the global epidemiology of pneumococcal diseases. Spawned surveillance data unequivocally showed strong decreases in IPD rates caused by the PCV serotypes. Simultaneously, serotype replacement by non-vaccine targeted serotypes occupying nasopharyngeal niches vacated after vaccination was observed. A recent example of this is the emergence of multidrug resistant serotype 35B in IPD isolates from USA and France (**Figure 1**) [5-7].

[figure not shown]

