1.3 The underdiagnosed and non-surveilled non-invasive population

Current national and international pneumococcal surveillance is strongly focused on IPD. However, it is now commonly accepted that NIPDs by far account as the major part of all pneumococcal infections worldwide. O'Brien and colleagues reported in 2009 that out of 14.5 million pneumococcal cases, 95.6% were cases of NIPD [1]. In a more recent meta-study by the Johns Hopkins School of Medicine, it was estimated that for every adult bacteraemia case there are at least three non-invasive pneumococcal infections [10], resulting in huge societal and economic costs [11].

Impelled by the lack of surveillance on NIPD, the majority of studies on pneumococcal vaccine effectiveness and serotype replacement are based on IPD data. However, **sheer extrapolation of IPD dynamics to NIPD has been called into question by recent studies**, using serotype-specific urinary antigen technology, which indicated discrepancy between persistent pneumococcal serotypes and the decline of the same serotypes causing IPD [12-14]. To get more insights in this matter, the Belgian Health Care Knowledge Centre (KCE) recently reviewed four observational studies from Denmark, Spain and Portugal (2), and the placebo arm of the CAPITA randomized controlled trial in the Netherlands [15-20]. In the infant populations of the study sites, PCV vaccine choice over time (PCV7, PCV10 and PCV13) and uptake differed. Three studies limited the detection of non-bacteraemic pneumonia to pneumonia with a positive culture of airway respiratory samples such as sputum or broncho-alveolar fluid, while the remaining study used both respiratory and urinary samples. Despite these differences, all studies concluded that the serotype distribution of bacteraemic and non-bacteraemic pneumococcal disease differed substantially in terms of vaccine serotype coverage (**Figure 2**) [15].

[figure not shown]

Figure 2. Proportion of serotype categories in bacteraemic/invasive pneumonia (BP) and non-bacteraemic/non-invasive pneumonia (NBP) in the Netherlands [16], Denmark [17], Spain [18] and Portugal [19,20]. Figure from the Belgian CSS/HGR rapport [15].

These results concurred with the few non-EU studies conducted in USA, Britain and Korea, showing that frequencies of vaccine serotypes among NIPD vary between 28.2 and 57.4%, depending on the specimen type and patient age [21-23].

[figure not shown]

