6.2 Evaluation

Our final goal is to investigate Belgian trends in serotype distribution in the non-invasive pneumococcal population. The statistical data analysis will be performed with Stat10 software (Stata Statistical Software: Release 13. College Station, TX), in collaboration with Sciensano's Epidemiology Service.

Using data from the Prospective/Retrospective surveillance track:

- Chi-square trend analysis of circulating serotypes within the non-invasive *S. pneumoniae* population, integrating retrospective data (1995-2014) with prospectively collected data (2020-2022). Data will be compared with the serotype dynamics of IPD, annually published by the NRC for pneumococcal diseases.

- Measurement of association strength within each stratum of age, gender and infection type by the prevalence ratios with exact Fisher tests for statistical significance. Particular attention will be given to NeSP isolates, their association with patient type and their influence on drug resistance.
- Chi-square trend analysis of antimicrobial resistance for all tested drug classes, in relation to historic data (1995-2013) and in association with serotype.
- Integrating metadata with WGS, we will perform phylogenetic analysis of sequenced isolates in their national and international context [13,14], and identification of genetic determinants of antibiotic resistance.

7 Access to source data and data in general

Neither of the funding partners can have a role in data collection and interpretation. However, funding partners can request at any time intermediate results or reports. The final report will be put under a six months embargo before open access publishing in Summer 2023.

8 Monitoring and quality assurance

All laboratory analyses will be performed according to ISO15089 standards. An internal project board consisting [name] (MD, PhD), [name] (Ir, PhD), [name] (Ir., PhD) and [name] (MD, PhD) will monthly follow up experimental results.

9 Adverse events

Not applicable.

10 Ethics

Upon approval of the project by at least two contact partners, a general and specific ethical application will be filed, in collaboration with Sciensano's legal department and GDPR officer. Approval of local and ethical committees will be sought.

11 Budget

PERSONNEL				
	Description	% Effort dedicated to this study	Institutional salary (3 years)	TOTAL
	Coordinating Scientist	0.6 FTE	€ 276,372	€ 165,823.2
	Statistician	0.2 FTE	-*	€ 0

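### Specimen site is not tied to diagnosis in 4.1, and 6.2 omits specimen type from its strata, so a change in specimen mix could pass for a serotype shift

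*Protocol*

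**What the plan says.** Two inclusion criteria in Protocol 4.1 matter here. One concerns the specimen: "from non-invasive upper (e.g.: pus/fluid from nasal sinus or from otitis media fluid) or lower respiratory tract", with the sites given as examples. The other concerns the patient: "from patients diagnosed with pneumonia, sinusitis and otitis". They stand as separate bullets, and no criterion links them. The background in 1.1 describes non-invasive disease more broadly: "pneumococcal isolates are typically isolated from superficial body sites such as ear, nose, sputum or other lower respiratory tract sites".

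The record sheet in 4.1 includes "sample source including collection method" and "clinical diagnosis", each supplied only where available.

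Section 1.3 reports from studies outside the EU that "frequencies of vaccine serotypes among NIPD vary between 28.2 and 57.4%, depending on the specimen type and patient age".

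In 6.2 the main analysis is a "Chi-square trend analysis of circulating serotypes within the non-invasive" population, combining the 1995-2014 isolates with those of 2020-2022. A further analysis is "Measurement of association strength within each stratum of age, gender and infection type", using prevalence ratios and Fisher tests. Infection type is not defined, and specimen source is not among the strata.

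Section 1.4 describes the historical collection as isolates from patients with community-acquired pneumonia and from children with acute otitis media. It does not mention sinusitis.

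**The concern.** The study aims to describe the serotypes that cause non-invasive disease (section 3). An isolate taken from a site other than the diagnosed one need not be the causal strain. Section 1.1 itself says that vaccination changes which serotypes occupy the nasopharynx, so colonising strains may follow vaccination in their own way.

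Two results could be affected:

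- **Infection-type contrasts.** If infection type is taken from the diagnosis alone, mismatched isolates enter the wrong stratum and blur the prevalence ratios.
- **The comparison over time.** If the specimen mix differs between the historical collection and 2020-22, the pooled vaccine-type share can move with no change in serotypes within any specimen type. Vaccination programmes changed over the same years, so the two explanations could not be separated without an analysis by specimen type.

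**Working it through.** **Reading the passages together**

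1. Eligibility. With only the specimens that 4.1 names, sputum from a patient with otitis meets both criteria, and so does sinus fluid from a patient with pneumonia. The example lists are open, so other upper-tract material is not excluded either. No rule says how to handle a mismatch.
2. Classification. Section 6.2 could assign infection type from the diagnosis, the specimen or both. Only the first would always place a mismatched isolate under the diagnosis. The protocol does not say which applies.
3. Strata. Section 1.3 names two factors on which vaccine-type frequency depends, specimen type and age. Section 6.2 stratifies on age and not on specimen type.
4. Mix over time. Section 1.4 names pneumonia and childhood otitis media for the historical collection; 4.1 also names sinusitis. A difference in mix is plausible, but the documents give no counts by specimen in either period.

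**Size**

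The protocol gives no figure on this point to reproduce. Inputs:

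- f, the share of discordant isolates: not in the documents; assumed 5%, 10%, 20%.
- d, the difference in vaccine-type share between discordant and concordant isolates: not in the documents; assumed 10 points. As an upper bound, the whole span in 1.3: 57.4 − 28.2 = 29.2 points.
- n = 2,250 for estimation and 1,500 per period for the comparison (6.1); vaccine-type share 50% (6.1: 7.5 + 7.5 + 5 + 30).

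Bias in one period = f × d. Between periods, only the difference in f counts: bias = (f₂ − f₁) × d, which is zero if the two periods have the same f and d.

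| f | d = 10 points | d = 29.2 points (upper bound) |
|---|---|---|
| 5% | 0.5 | 1.46 |
| 10% | 1.0 | 2.92 |
| 20% | 2.0 | 5.84 |

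For scale, the 95% half-width for a 50% class is 1.96 × √(0.5 × 0.5 / 2,250) = 2.07 points. If the 20% change in 6.1 is relative, the change sized for is 0.20 × 50 = 10 points.

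Chance of declaring a shift when there is none, with 1,500 per period, a two-sided 5% test and discordant isolates in one period only: the standard error is √(2 × 0.25 / 1,500) = 1.83 points. With a bias of 2.0 points, z = 2.0 / 1.83 = 1.10 and the chance is about 0.20. At d = 10 points the chances are 0.06, 0.09 and 0.20 for f = 5%, 10% and 20%. At d = 29.2 points they are 0.13, 0.36 and 0.89.

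**The case against.** The strongest reply is that the documents do not show the problem occurring. Every specimen that 4.1 gives as an example is material from an infection site: sinus pus or fluid, middle-ear fluid, sputum, aspirates, lavage. The record sheet captures source and diagnosis, so mismatches can be found where the fields are filled. Strata and sensitivity analyses are often left to a statistical analysis plan, which is not at hand. Most of this stands and limits the point. What remains is that 6.2 already lists its strata and leaves out a factor that the protocol's own rationale names, and that it uses infection type without defining it.

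Three stronger readings are tempting and are not supported:

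- *A nose isolate from a pneumonia patient is counted as a pneumonia serotype.* A nasal swab is not named in 4.1. It enters only through the open example list and a background sentence in 1.1. How it would be counted is unknown while infection type is undefined, and the main trend analysis states no separate pneumonia count.
- *Section 6.2 stratifies by infection type alone.* It names age and gender as well.
- *A false shift is likely, with probability up to 0.89.* That figure needs 20% discordance, all of it in one period, and a 29.2-point difference. The 29.2 points span several studies and countries, and mix age with specimen type; they do not contrast discordant with concordant isolates.

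A further objection concerns the remedy. Requiring site and diagnosis to match in 4.1 would restrict the prospective track only, because the retrospective isolates come from an existing archive. That could create the difference in mix that it is meant to prevent. This stands, and the change proposed below avoids it.

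**Conclusion.** The point holds as a gap in definition and analysis. The protocol allows site and diagnosis to disagree, does not say how such isolates are classed, and does not plan the historical comparison by specimen type.

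On the moderate assumptions (5-20% discordance, 10-point difference) the bias is 0.5 to 2.0 points. That is no larger than the 2.1-point half-width for the whole sample, and at most a fifth of a 10-point change. Within an infection-type stratum the interval is wider still. The 5.84-point case is only an upper bound. Neither the discordant share nor the difference by specimen can be taken from the documents, so the true size is unknown and may be negligible. The change is worth making because it costs little and protects the main trend result from an alternative explanation.

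**What to change.** In 6.2:

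1. Define infection type from clinical diagnosis and specimen source together.
2. Add specimen type to age, gender and infection type as a stratum.
3. Stratify the retrospective-prospective comparison by specimen type, or standardise it to a common specimen mix, where source is recorded in both tracks.
4. Flag isolates whose specimen site and diagnosis disagree, and report a sensitivity analysis restricted to concordant isolates, with the same rule in both tracks.

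Leave eligibility in 4.1 as it is, so that the two tracks are not made less comparable.

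The cost is a few sentences, since both fields are already on the prospective record sheet. The strata become smaller and their estimates less precise. Isolates with a blank source or diagnosis drop out of these analyses, so their number should be reported for each track. The adjusted historical comparison also depends on how fully source was recorded in the archive, which the protocol does not say.

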1.4 Sciensano holds historical collection of non-invasive pneumococcal isolates

Between 1995 and 2015, [name] (MD, PhD) led a team at Sciensano investigating the evolution of antibiotic resistance in NIPD isolates from CAP patients (as well as from children with acute otitis media). For 12 consecutive winter periods, his team collected between 300 and 500 clinical isolates using a network of 15 peripheral hospital-based laboratories distributed across the country. Consequently, we hold a collection of >5,000 strains for which extracted gDNA, complete phenotypic MIC profiles and associated metadata are already available (**Figure 4** for age distribution). This study, funded by Bayer, focused on antimicrobial resistance and did not routinely include serotyping.

This constitutes an extremely valuable collection that dates from before the introduction of pneumococcal vaccination programs. In the context of the proposed study, this collection would serve to retrospectively assess the impact of successive vaccination campaigns on serotype distribution among NIPD isolates in Belgium.

[figure not shown]

Figure 4. Age distribution of the patients for which cultures were included during the NIPD surveillance study in 2012-2013 using the same network of laboratories [24].

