4.2 Retrospective track

As described in Section 1.4, Sciensano holds a collection of >5,000 NIPD strains (1995-2015) for which extracted gDNA, complete MIC profile and associated metadata are already available. From every uneven year, we will randomly select 150 isolates, without bias towards age and gender. On these strains, we will perform FT-IR capsular typing, which will have been developed during the first months of this project (section 5.4). Typing of the isolates of the retrospective study will be performed in the summer period of 2021, when few isolates of the ongoing prospective study (2020-2022) are expected.

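### The exclusion of patients with a simultaneous sterile-site isolate is written only for the prospective track, so the between-period PCV13-type shift may be partly a change of case definition

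*Protocol*

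**What the plan says.** Section 4.1 (Prospective track) gives one exclusion criterion: patients for whom S. pneumoniae "was simultaneously isolated from blood or another usually sterile specimen". It works on the patient, not on the specimen.

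Section 4.2 (Retrospective track) gives one selection rule: "From every uneven year, we will randomly select 150 isolates, without bias towards age and gender". It does not refer back to the 4.1 exclusion. Section 1.4 describes the source as more than 5,000 strains from a resistance survey in pneumonia patients and in children with otitis media. Both sections call the strains NIPD. Neither states the survey's eligibility criteria or says how patients with a positive blood culture were handled.

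Section 6.1 sizes the comparison of PCV13 types between 1995-2015 and 2020-2022 at 1,500 isolates per time point. Section 6.2 puts the two tracks into one chi-square trend analysis.

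Two background statements bear on this. Section 1.1 says that "a substantial proportion (10-20%) of CAP pneumonia" due to the pneumococcus comes with bacteraemia. Section 1.3 reports, from the studies it reviews, that "the serotype distribution of bacteraemic and non-bacteraemic pneumococcal disease differed substantially in terms of vaccine serotype coverage".

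**The concern.** The between-period comparison needs the same kind of isolate on both sides. As written, a sputum isolate from a bacteraemic pneumonia patient cannot enter the 2020-2022 sample, while nothing in 4.2 keeps such an isolate out of the historical one. If such isolates are in the collection, the case definition changes at exactly the step between the two tracks, which is the contrast the study wants to read against the vaccination programmes. Typing more isolates would not remove the difference. The planned comparison with the IPD series would also be blurred, because some historical non-invasive isolates would come from patients who also count as invasive cases.

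Eligibility is fixed in 4.1 and 4.2, and the draw comes before any analysis. An analysis plan could add a sensitivity analysis, but it could not make the two samples comparable after the isolates have been drawn and typed.

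**Working it through.** **The plan's own figures.** Section 6.1 gives PCV7 types 7.5%, 19A 7.5%, serotype 3 5% and four further PCV13 types 30%. The PCV13 share is therefore 7.5 + 7.5 + 5 + 30 = 50%. The stated size is 1,500 per time point to detect a 20% decrease. That size is not reproduced from a 50% baseline: 50% to 40% needs 388 per period (80% power, two-sided 5%) and at most 661 in the variants tried. This is a separate matter. The 1,500 is used here only to obtain the standard error of the comparison as planned.

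**Standard error of the difference.** At 50% and 1,500 per period: sqrt(0.25 × 2/1500) = 0.0183, or 1.83 points.

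**Form of the bias.** Let f be the share of the historical draw that comes from bacteraemic patients, and d the PCV13-type share in bacteraemic minus non-bacteraemic isolates. The expected historical share is then the non-bacteraemic share plus f × d. The prospective sample has f = 0 by rule. With no true change, the apparent difference is f × d.

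**Inputs.**
- f: section 1.1 gives 10-20% for pneumococcal CAP. It carries over to the whole draw only if the survey applied no exclusion and the draw is mostly pneumonia isolates. It is 0% if the survey did exclude such patients.
- d: the text gives no figure and no sign. Values of 10 and 20 points are assumed.

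**Results** for a simple two-period z-test with no true change. The rejection rate is P(|Z + bias/SE| > 1.96).

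| f | d (assumed) | bias | rejection rate |
|---|---|---|---|
| 0% | any | 0 | 5% |
| 10% | 10 points | 1.0 point | 8.5% |
| 20% | 10 points | 2.0 points | 19.5% |
| 10% | 20 points | 2.0 points | 19.5% |
| 20% | 20 points | 4.0 points | 59% |

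If d is negative, the bias has the opposite sign and the rates are practically the same. For the 2-point case, bias/SE = 2.0/1.83 = 1.1.

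**Against the planned effect.** If the 20% decrease is relative, it is 50% × 0.20 = 10 points, and a 2-point bias is one fifth of it. The protocol does not say whether the 20% is relative or absolute.

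**Room for the exclusion.** Section 1.4 gives 300 to 500 isolates per winter. Removing 20% from the smallest yield leaves 300 × 0.80 = 240, which still covers 150.

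**The case against.** A reader might infer that the shift is biased. The documents do not support that. Bias requires bacteraemic patients in the historical collection, and no section says they are there. The strains are called non-invasive or NIPD throughout, so the survey may have applied an equivalent exclusion; its criteria are not in the protocol. This objection stands, and it limits the point to what the protocol fails to establish.

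A reader might also infer that sections 1.1 and 4.1 contradict each other, since 1.1 says the distinction "relates to the laboratory diagnosis and anatomical sites from which pneumococci are isolated" while 4.1 works by patient. Section 1.1 is background, describes where isolates typically come from, and is silent on patients positive at both kinds of site. Section 4.1 can be read as settling that overlap. This is a gap, not a contradiction.

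The size can fairly be challenged too. The 10-20% refers to pneumonia, so otitis isolates lower f. The difference d is an assumption, and its sign is unknown. If the true shift were 10 points, power at 1,500 per period would exceed 99.9%, so a 2-point bias would distort the estimate without creating the finding. All of this stands. It leaves open that a small or absent shift could be misread, and that every estimated shift would carry the error.

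Finally, the check may not be possible for every isolate. The protocol does not list the fields held for the historical strains, and the prospective record sheet in 4.1 has no blood-culture item. The fix has to allow for unknown status.

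**Conclusion.** The point holds as a gap in eligibility. The sterile-site exclusion is stated for one side of a comparison and not for the other, and the protocol does not show that the earlier survey applied it. If it did not, part of the between-period PCV13-type shift may come from case mix. The protocol's statements on concurrent bacteraemia and on serotype coverage make this plausible, but they give neither the size nor the direction.

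The bias is zero if the survey already excluded such patients. The 2-point example, with rejection near 20% in place of 5%, rests on a 20% share, an assumed 10-point difference, a 50% baseline and 1,500 isolates per period. It shows why the gap is worth closing; it is not an estimate. The change should be made because it is cheap and has to come before the draw.

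**What to change.** In section 4.2, state the eligibility criteria of the historical survey and say whether they already covered the 4.1 exclusion. If records show that they did, one sentence closes the point.

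Otherwise, apply the 4.1 exclusion to the historical isolates before the random draw, wherever survey records or metadata show sterile-site status.

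Where that status is unknown, report the between-period shift with a sensitivity range for the pneumonia isolates only. Start at 0% from bacteraemic patients and go up to 20%. The NRC's IPD series, which 6.2 already plans to use, can supply the serotype mix for that share. Acknowledge it as a rough proxy, because IPD also includes meningitis and other sterile-site disease. Qualify the conclusion according to how far the shift moves across the range.

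The cost is a short addition to 4.2, a check of whatever records exist and a small extra analysis. A few historical isolates would be replaced in the draw, and the reported range would be wider where status is unknown. The planned 150 per selected year need not change.
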